10.2 Sample Size and Accrual

We propose to enroll ten subjects in this pilot study. The expected accrual rate is 7 subjects over approximately 4 months. The primary endpoint is safety and tolerability of enzalutamide when combined with GnRH agonist and radiation therapy. Descriptive statistics will be computed to assess safety and tolerability. The highest AE score for each category over the 12 month period following initiation of treatment with enzalutamide plus GnRH agonist will be reported for each study subject in the summary statistics. Secondary endpoints assess mechanisms of enzalutamide plus GnRH action on prostate cancer tissue and quantitative imaging of localized prostate cancer response to enzalutamide plus GnRH therapy. As this is a pilot study, statistics will be used to report outcomes.

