kV	Kilovoltage		
LDH	Lactate Dehydrogenase		
MG (or mg)	Milligram		

ML (or mL)	Milliliter		
MRI	Magnetic Resonance Imaging		
MV	Megavoltage		
NCCN	National Comprehensive Cancer Network		
NCI	National Cancer Institute		
NG (or ng)	Nanogram		
PK	Pharmacokinetics		
PSA	Prostate Specific Antigen		
PD	Progressive Disease		
PFS	Progression Free Survival		
p.o.	peros/by mouth/orally		
PR	Partial Response		
PTV	Planning Target Volume		
qRT-PCR RTOG- ASTRO	Quantitative Reverse Transcription Polymerase Chain Reaction Radiation Therapy Oncology Group – American Society for Therapeutic Radiology and Oncology		
SAE	Serious Adverse Event		
SD	Stable Disease		
SGOT	Serum Glutamic Oxaloacetic Transaminase		
SPGT	Serum Glutamic Pyruvic Transaminase		
T1/2 (or t1/2)	Half-life		
TRUS	Transrectal Ultrasound		
WBC	White Blood Cells		

STUDY SCHEMA

STUDY SUMMARY

Title	Phase II pilot study of enzalutamide (MDV3100) and gonadotropin- releasing hormone (GnRH) agonist before, during, and after radiation therapy in treatment of patients with high-risk localized prostate cancer	
Short Title	Phase II trial of radiation with enzalutamide (MDV3100) and androgen deprivation	
Protocol Number	The standard protocol number used to identify this study	
Phase	2	
Methodology	Open label	
Study Duration	5 years	
Study Center(s)	Single-center	
Objectives	This is a single institution phase II trial studying the safety and efficacy of combined enzalutamide and GnRH agonist therapy administered with EBRT for high-risk and locally advanced prostate cancer.	
Number of Subjects	7	

Diagnosis and Main Inclusion Criteria	 Patients must be candidates for long-term androgen deprivation in combination with EBRT for the treatment of high-risk or locally-advanced prostate cancer by the following criteria: High risk disease: T3a or Gleason 8-10 or serum PSA > 20 ng/mL Gleason 7 also allowed if > 50% of cores positive for cancer or PSA velocity > 2 ng/mL/year in preceding 12 months Locally advanced (very high risk) disease: T3b-T4 Patients may have radiographic evidence of metastasis in regional lymph nodes (N1 disease as defined by the National Comprehensive Cancer Network Prostate Cancer Guideline Verson 3.2012) at the discretion of the treating physicians, if regional lymph nodes can be included in the planned radiation field. 	
Study Product(s), Dose, Route, Regimen	Enzalutamide (MDV3100) (Xtandi), 4 x 40 mgcapsules (160 mg total) by mouth daily	
Duration of administration	6 months	

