4.4.1.7.2 Radiation Quality Assurance Review

The study's radiation PI or his designees will perform an RT Quality Assurance remote review after complete data for the first 4 of the cases enrolled has been made available. The study PI or his designees will perform the next remote review after complete data for the next 3 cases have been enrolled. The final cases will be reviewed within 3 months after this study has reached the target accrual or as soon as complete data for all cases enrolled has been made available, whichever occurs first. These reviews will be ongoing and performed remotely.

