4.8 Subject Replacement

If a subject is withdrawn from the study prior to the initiation of radiation therapy for reasons other than AEs as outlined in tables 4.2.1 and 4.2.2, an additional subject may be added to the study.

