7.7 Stopping Rules

Based on experience from a completed phase III study, enzatlutamide is generally well tolerated when given in combination with a GnRH agonist. The most prominent safety concerns are primarily related to the risk of seizures. No completed study has examined the combination of enzalutamide with a GnRH agonist and concurrent radiation. The general tolerability of this combination is anticipated to be similar to that of radiation with concurrent GnRH agonist therapy. However, the absence of unexpected adverse events must be verified and is the primary endpoint of this study. Adverse events will be measured by NCI CTCAE criteria and will be monitored and recorded for a period of 12 months from initiation of the combination of enzalutamide plus GnRH agonist. Enrollment in the trial will be halted if unacceptable levels of toxicity are found as defined by 3 or more patients withdrawing from the study due to AEs.

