10.0 STATISTICAL CONSIDERATIONS

10.1 Study Design/Study Endpoints

This is an open-label, single-arm, single-center prospective pilot study of enzalutamide plus GnRH agonist treatment combined with EBRT in the treatment of men with high-risk localized or locally advanced prostate cancer. Select patients with regional lymph node involvement (N1 disease) are also eligible to participate in this study.

Primary endpoint: to determine the safety and tolerability of combining enzlutamide plus a GnRH agonist with EBRT up to 12 months following initiation of treatment with enzalutamide plus GnRH agonist.

Secondary endpoints:

1. Molecular markers of androgen signaling and cell death in prostate biopsy samples

- a. Inhibition of androgen-regulated gene expression (potential targets to include NDRG1, FKBP5, TMPRSS2, and PSA) by qRT-PCR
- b. Inhibition of androgen receptor (AR) nuclear localization and enhancement of apoptotic cell death measured by immunohistochemistry (IHC)
- c. Androgen metabolism in prostate biopsy samples
- 2. Serum PSA, testosterone, dehydroepiandrosterone (DHEA), and DHEA-sulfate (DHEA-S) following combination therapy with enzalutamide plus GnRH agonist therapy prior to initiation of radiation therapy
- 3. Changes in prostate tumor volume and activity following 2 months of combined enzalutamide plus GnRH therapy compared to baseline as measured by multiparametric magnetic resonance imaging (MRI)

The trial will be halted if unacceptable levels of toxicity are found as defined by 3 or more patients withdrawing from the study due to AEs or if 3 or more patients experience SAEs.

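### The plan states two enrollment targets, 7 and ten, and two halting rules that differ in trigger and in consequence

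*Combined protocol and SAP*

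**What the plan says.** **Sample size.** In the Study Summary table, the row "Number of Subjects" has the value 7. Section 10.2 states "We propose to enroll ten subjects in this pilot study" and continues: "The expected accrual rate is 7 subjects over approximately 4 months". Three other places bear on the total without stating one:

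- Section 4.8: after certain withdrawals before radiation, "an additional subject may be added to the study".
- Section 4.4.1.7.2: radiation plans are reviewed once data for the first 4 cases are complete, and again "after complete data for the next 3 cases have been enrolled".
- The same section: "The final cases will be reviewed within 3 months after this study has reached the target accrual".

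**Halting rule.** Section 7.7 reads "Enrollment in the trial will be halted if unacceptable levels of toxicity are found as defined by 3 or more patients withdrawing" because of AEs. Section 10.1 halts the trial, rather than enrollment, on "3 or more patients withdrawing from the study due to AEs or if 3 or more patients experience SAEs".

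**The concern.** Safety over 12 months is the primary endpoint and the analysis is descriptive. The number of patients and the halting rule are therefore most of the design, and each exists in two current forms.

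Section 11.4 requires the study to be run as the protocol describes, which cannot be done for a total described in two ways. The target accrual that sets the last quality assurance deadline in 4.4.1.7.2 is undefined for the same reason.

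On halting, three patients who have SAEs but stay on study stop the trial under 10.1 and trigger nothing under 7.7. The 7.7 consequence also has something to stop only while enrollment is open, and most of the safety observation comes later.

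**Working it through.** **1. Can 7 and ten be reconciled?**

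The documents give no precision target, power or dropout rate, so neither figure can be reproduced. The possible explanations are:

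- *Accrual.* 7 in about 4 months is 7/4 = 1.75 per month. Ten would take 10/1.75 = 5.7 months. The sentence is a rate and fits either total.
- *Replacement.* Section 4.8 is optional, has no cap and cites neither figure. Reaching ten from 7 by dropout inflation needs 7/(1 − 0.30) = 10, a 30% loss that is stated nowhere.
- *Quality assurance batches.* 4 + 3 = 7. A further group of final cases suggests more than 7 but gives no number. If the total is 7, none remain unless replacements are counted as extra cases.

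None of these settles the total.

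**2. What the difference is worth**

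- Size: 10/7 = 1.43.
- If no patient has a given event, the one-sided 95% upper bound on its rate is 1 − 0.05^(1/n): 34.8% for n=7 and 25.9% for n=10.
- Three patients are 3/7 = 42.9% or 3/10 = 30.0% of the study.

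**3. How far apart the halting rules are**

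Let W be the probability of 3 or more AE withdrawals and S the probability of 3 or more patients with SAEs. Each is a binomial tail, P(X ≥ 3) with X ~ Bin(n, p), if all n patients are observed.

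- The 7.7 trigger has probability W.
- The 10.1 trigger has probability S if every AE withdrawal is in a patient with an SAE, and 1 − (1 − W)(1 − S) if the two events are independent.

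Worked case, n=7 with 10% AE withdrawal and 20% SAE:

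- W = 1 − 0.4783 − 0.3720 − 0.1240 = 0.0257
- S = 0.1480
- Under independence, 1 − 0.9743 × 0.8520 = 0.1699

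| AE withdrawal / SAE rate | n | 7.7 trigger | 10.1 trigger (nested to independent) |
|---|---|---|---|
| 5% / 10% | 7 | 0.4% | 2.6–2.9% |
| 5% / 10% | 10 | 1.2% | 7.0–8.1% |
| 10% / 20% | 7 | 2.6% | 14.8–17.0% |
| 10% / 20% | 10 | 7.0% | 32.2–37.0% |
| 15% / 30% | 7 | 7.4% | 35.3–40.1% |
| 15% / 30% | 10 | 18.0% | 61.7–68.6% |
| 7.6% / 33.5% | 7 | 1.2% | 43.3–44.0% |
| 7.6% / 33.5% | 10 | 3.5% | 70.5–71.5% |

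The first three rate pairs are assumptions. The last pair comes from the earlier phase 3 trial described in section 1.2.2 (drug discontinuation for AEs, and SAEs). That trial enrolled patients with castration-resistant disease after docetaxel, and stopping the drug is not the same as leaving the study, so this pair is also only illustrative.

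**4. When an enrollment halt can act**

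Assume one patient every 4/7 month, each treated from enrollment and observed for 12 months. When the last patient enrolls, the follow-up accrued is (4/7) × (0 + 1 + … + (n − 1)):

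- n=7: (4/7) × 21 = 12.0 of 7 × 12 = 84 patient-months, 14%
- n=10: (4/7) × 45 = 25.7 of 10 × 12 = 120 patient-months, 21%

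If the 7 patients are instead spread over the full 4 months, the spacing is 4/6 month and the figure is (4/6) × 21 = 14 of 84, or 17%.

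**The case against.** The strongest reply accepts that the texts differ and disputes the consequences.

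- *The planned number is not the analysis denominator.* Section 6.2 analyzes all subjects who received at least one dose, and no test or decision threshold depends on the planned total. This is right as far as it goes: the direct defect is an unclear enrollment ceiling. But the number treated follows from the number enrolled, so the safety denominator still depends on which figure the site uses.
- *The halting rules are not mutually exclusive.* 10.1 contains the 7.7 trigger and adds one, and halting a trial also halts its enrollment, so a site that follows 10.1 also meets 7.7. That is true, but a site that works from 7.7, the section headed as the stopping rules, would miss the SAE trigger.
- *SAEs are overseen anyway.* Under 7.3.5 and 11.3 the data safety monitoring committee receives all local SAEs, its chair reviews them on receipt, and it can act at once. Three patients with SAEs would not go unnoticed. That review is discretionary, however, and does not say which written rule binds.
- *The figures rest on assumptions.* The event rates are assumed, and the timing percentages shift with patient spacing and with the gap between enrollment and first dose, because the clock in 4.6 starts at treatment. The direction is secure: 10.1 can never be triggered less often than 7.7. The percentages should be read as illustrations.

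**Conclusion.** Both conflicts are confirmed by the text. The enrollment target is 7 or ten, a 43% difference, and nothing in the document decides between them. This part needs no assumption.

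The halting rules in 7.7 and 10.1 differ in trigger and in consequence, and this does not depend on which total is meant. Over the rates tabulated, the 10.1 trigger is met several times as often as the 7.7 trigger. That size rests on the assumed rates, the two overlap assumptions and complete observation of all patients. An enrollment-only halt would come too late for most of the observation period, given roughly even accrual at the stated rate.

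A sample size and a safety decision rule that the study relies on are wrong as written and must be corrected. The documents do not show which total or which rule was intended.

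**What to change.** 1. State one number of subjects in the Study Summary and in 10.2, with the matching accrual time: about 4 months for 7, or about 5.7 months for ten at the stated rate.
2. Say in 4.8 and 10.2 whether replacement subjects count toward that number.
3. If the number is 7, revise the review batches in 4.4.1.7.2. If it is ten, they can stand.
4. Reconcile 7.7 and 10.1 so that both give the same trigger or triggers and the same consequence. Which rule applies is for the sponsor and the investigator to decide.

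The cost is wording in these sections and, under 11.5, a written amendment approved by the IRB before implementation. The analysis does not change, and no patients are added beyond the number the sponsor intends.

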10.3 Data Analyses Plans

Primary endpoint: to determine the safety and tolerability of combining enzlutamide plus a GnRH agonist with EBRT up to 12 months following initiation of treatment with enzalutamide plus GnRH agonist. Data analysis plan: descriptive statistics to report the number and nature of AEs in all patients over 12 months.

Secondary endpoints:

- 1. Molecular markers of androgen signaling and cell death in prostate biopsy samples will be analyzed using descriptive statistics
 - a. Inhibition of androgen-regulated gene expression (potential targets to include NDRG1, FKBP5, TMPRSS2, and PSA) by qRT-PCR
 - b. Inhibition of androgen receptor (AR) nuclear localization and enhancement of apoptotic cell death measured by immunohistochemistry (IHC)
 c. Androgen metabolism in prostate biopsy samples
- 2. Serum PSA, testosterone, dehydroepiandrosterone (DHEA), and DHEA-sulfate (DHEA-S) following combination therapy with enzalutamide plus GnRH agonist therapy prior to initiation of radiation therapy will be reported using descriptive statistics for each patient.
- 3. Changes in prostate tumor volume and activity following 2 months of combined enzalutamide plus GnRH therapy compared to baseline as measured by multi-parametric magnetic resonance imaging (MRI) will be reported using descriptive statistics for each patient and summarized with mean change and standard deviation.

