2.0 STUDY OBJECTIVES

2.1 Primary Objectives

2.1.1 To determine the safety and tolerability of combining enzalutamide 160 mg by mouth daily with a GnRH and EBRT. Enzalutamide and GnRH agonist will be administered in combination for 6 months, beginning two months prior to the start of EBRT. Enzalutamide and GnRH agonist treatment will continue for the duration of EBRT and for approximately two months after completion of EBRT, for a total of 6 months of combined enzalutamide plus GnRH treatment. Patients will subsequently receive an additional 18 - 30 months of GnRH agonist therapy for a total of two - three years of GnRH agonist treatment. Safety and tolerability will be assessed by frequency and severity of adverse events with monthly monitoring for 12 months following initiation of enzalutamide plus GnRH therapy.

Secondary Objectives

2.1.2 To determine whether enzalutamide combined with GnRH agonist treatment inhibits intra-tumoral androgen-regulated gene expression (potential targets to include NDRG1, FKBP5, TMPRSS2, and PSA) as measured by qRT-PCR

- 2.1.3 To determine whether enzalutamide combined with GnRH agonist treatment impairs androgen receptor nuclear localization and cancer cell proliferation in targeted prostate cancer biopsy samples.
- 2.1.4 To determine the impact of enzalutamide combined with GnRH agonist on androgen metabolism in prostate biopsy samples.
- 2.1.5 To determine the impact of enzalutamide plus GnRH agonist therapy on serum prostate specific antigen (PSA) and testosterone following two months of treatment.
- 2.1.6 To describe any preliminary evidence of anti-tumor activity by assessment of objective response as determined by multiparametric MRI in patients with high-risk localized or locally-advanced prostate cancer.

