2.2 Exploratory Objectives

Exploratory objectives are those defined above as secondary objectives 2.1.2 – 2.1.4.

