9.0 CORRELATIVES/SPECIAL STUDIES

The goal of the planned laboratory correlative studies is to evaluate the proposed mechanism of action of enzalutamide plus GnRH agonist on patient tumor samples. The proposed mechanism of action of enzalutamide has been established in pre-clinical studies. However, to date the molecular mechanism of action has not been reported in primary prostate cancer tumors from

patients. The purpose of the proposed laboratory correlative studies is to examine androgen signaling inhibition by enzalutamide in primary tumor samples from patients. Submission of samples for correlative studies is mandatory for participation in this trial.

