9.1 Sample Collection Guidelines

Up to 6 needle core biopsies will be collected using 18 gauge needles under TRUSguidance at each of two occasions as described in Section 4.4.2.2. Biopsies will be performed at study entry and following 8 weeks of treatment with combined enzalutamide plus GnRH agonist. Samples will be submitted to pathology laboratory for diagnosis and to UTSW tissue bank. Samples will be labeled with the subject's de-identified study number and collection date and delivered for analysis to:

[name], MD

Cleveland Clinic and also to [name] and [name] at UT Southwestern Medical Center.

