9.2.2 Gene expression studies

Ligand-bound androgen receptor (AR) activity may be defined by the expression of androgen-responsive genes. *PSA*, *TMPRSS2* and *FKBP5* are among the most widely studied and validated among these genes.²⁴ RNA will be extracted from the collected prostate cancer tissue using the RNeasy system (Qiagen, Germantown, MD), and 1 µg RNA will be used in a reverse transcription reaction using the iScript cDNA Synthesis Kit (Bio-Rad, Hercules, CA). Quantitative-PCR (qPCR) analysis will be performed in triplicate using previously published primers for *PSA*, *TMPRSS2*, *FKBP5* and for the housekeeping gene *large ribosomal protein P0* (*RPLP0*).²⁵ Absolute qPCR SYBR Low Rox Mix (Fisher, Waltham, MA) will be used in 25 µl final reaction volume, in 96-well plates. The thermocycling reaction will carried out in an ABI 7500 Real Time PCR machine (Applied Biosystems, Foster City, CA). Accurate quantitation of each mRNA will be achieved by normalizing the sample values to *RPLP0* and to vehicle treated cells. Samples will be labeled with the subject's de-identified study number and collection date and delivered for gene expression analysis to

[name]. Kendrick Family Endowed Chair for Prostate Cancer Research Cleveland Clinic Lerner Research Institute Cancer Biology, NB40 [name]

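### The biopsy-marker analysis in 10.3 names no within-patient change, samples reach the laboratories showing their collection date, and the gene list and the wording in 9.0 need closing

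*Combined protocol and SAP*

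**What the plan says.** The gene-expression objective, 2.1.2, is "To determine whether enzalutamide combined with GnRH agonist treatment inhibits intra-tumoral androgen-regulated gene expression". Objective 2.1.3 asks the same kind of question about AR nuclear localization and proliferation. Section 2.2 then states: "Exploratory objectives are those defined above as secondary objectives", covering 2.1.2 to 2.1.4, while 10.1 and 10.3 keep the biopsy markers as secondary endpoints.

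The only analysis given is item 1 of 10.3: "Molecular markers of androgen signaling and cell death in prostate biopsy samples will be analyzed using descriptive statistics". In the same list, serum markers (item 2) are reported for each patient, and MRI change (item 3) "will be reported using descriptive statistics for each patient and summarized with mean change and standard deviation".

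Under 9.1, samples are labelled with the "de-identified study number and collection date and delivered for analysis to" the named laboratories. Sections 9.2.2 and 9.2.3 repeat that labelling. Section 9.2.1 has AR and Ki-67 slides read under a light microscope and mentions neither masking to time point nor a scoring scale.

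The gene list in 10.1 is "potential targets to include NDRG1, FKBP5, TMPRSS2, and PSA". Section 9.2.2 says "Quantitative-PCR (qPCR) analysis will be performed in triplicate using previously published primers for" PSA, TMPRSS2, FKBP5 and the housekeeping gene RPLP0. Section 9.0 gives the purpose as to "examine androgen signaling inhibition by enzalutamide in primary tumor samples from patients".

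**The concern.** The design is built for a before-and-after comparison within each man: biopsies at baseline and after about two months (2.3), repeat sampling of the same sites (4.4.2.2) and co-registration of the two biopsies (6.1.2.5). The analysis section does not say that the comparison will be made. Up to 6 cores are taken per man per occasion, and no rule says how they become one value.

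Two kinds of bias are left open. A reader who knows that a slide is post-treatment may score it lower for nuclear AR or Ki-67, in the direction of the hypothesis. And if a man's two samples are assayed in different runs, any run-to-run difference becomes part of his apparent change.

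Two gaps affect interpretation. An open gene list leaves room to choose which genes count as AR signaling. Wording that credits enzalutamide alone invites a claim the design cannot support. Section 1.4 says the results will prepare for randomized trials, and 9.0 makes the research samples mandatory, so the tissue deserves a defined analysis.

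**Working it through.** **No figure to reproduce.** The documents give no power, significance level, effect size or standard deviation for these endpoints. Sample size is stated as 7 (Study Summary; accrual sentence of 10.2) and as 10 (10.2), so both are used below.

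**The three secondary analyses in 10.3, side by side**

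| Item | Per-patient report stated | Change from baseline stated | Summary stated |
|---|---|---|---|
| 1. Biopsy markers | no | no | descriptive statistics |
| 2. Serum PSA and hormones | yes | no | descriptive statistics |
| 3. MRI volume and activity | yes | yes | mean change and SD |

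**What pairing would deliver.** For a mean within-man change over n pairs, the 95% half-width in units of the SD of the change is t(0.975, n−1)/√n.

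| Pairs | Calculation | Half-width (SD of change) |
|---|---|---|
| 10 | 2.262/3.162 | 0.715 |
| 7 | 2.447/2.646 | 0.925 |
| 6 (assumed loss) | 2.571/2.449 | 1.049 |
| 5 (assumed loss) | 2.776/2.236 | 1.242 |

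As a gauge only, assume a two-sided 5% paired t-test with 80% power (neither is in the documents). The noncentral t distribution then gives a detectable change of 1.27 SD with 7 pairs and 1.00 SD with 10. Large, consistent changes would show; smaller ones would not.

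**Testing marker by marker.** Unadjusted 5% tests, assuming independent genes, give a chance of at least one false positive of 1 − 0.95³ = 14.3% for three genes and 1 − 0.95⁴ = 18.5% for four. This favors one summary over the gene set.

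**Genes.** Four are named in 10.1 and 10.3 (NDRG1, FKBP5, TMPRSS2, PSA). Three have primers in 9.2.2. NDRG1 is the mismatch.

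**Attribution.** Both drugs start together in a single arm (2.1.1, 4.1). Section 8.2 says GnRH agonists reduce serum testosterone, and 9.2.2 treats these genes as a readout of ligand-bound AR. A fall in expression could therefore come from either drug.

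**The case against.** The strongest reply is that these are correlates in a small pilot, that 2.2 calls the objectives exploratory, and that the Study Summary plans descriptive statistics for the biological correlates throughout. That stands as far as hypothesis tests go: none is needed. It does not remove the gap, because a per-man change with an interval is itself descriptive, and the MRI item already plans a mean change.

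Several stronger readings are tempting but unsupported:

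- *The plan compares group averages and ignores pairing.* Item 1 states neither group nor patient level; the contrast with items 2 and 3 is only suggestive. It would also be wrong to measure the harm as precision lost against an unpaired analysis, since no unpaired analysis is planned.
- *The question cannot be answered.* The paired data will exist. If all 7 men changed in the same direction, an exact two-sided sign test would give 2/2⁷ = 0.016. With 5 pairs (assumed) the floor is 2/2⁵ = 0.0625.
- *Date labels break the pairing.* The label also carries the subject number, so pairs can be linked. The fault is that time point is visible.
- *Genes can be picked freely afterwards.* Section 9.2.2 names three specific primer sets, so the freedom is limited. The open wording and NDRG1 remain.
- *The whole correlative program credits enzalutamide alone.* The objectives and endpoints refer to the combination, as does the opening sentence of 9.0. The hypothesis in 1.5 is also set in combination with the GnRH agonist. The fault is one sentence of 9.0.

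On assay bias, 9.2.2 already has triplicates and RPLP0 normalization, and the documents give no figure for run-to-run error. Running pairs together is thus a low-cost safeguard, not the cure of a shown defect. Masking matters most for the IHC reading, which rests on judgment.

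**Conclusion.** The point holds as a gap in specification that is cheap to close. Section 10.3 item 1 does not commit to within-man change, the labels expose time point with no masking stated, NDRG1 has no assay in 9.2.2, and one sentence of 9.0 claims more than a single arm can show. As written, a later claim of inhibition would be weakly supported.

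With all pairs evaluable, the proposed interval would have a half-width of 0.925 SD of the change (7 men) or 0.715 SD (10 men), assuming changes roughly normal on the analysis scale. Fewer evaluable pairs widen it. The size of any reader or run bias cannot be calculated from the documents. Because the objectives are also declared exploratory, this is a recommended improvement and does not threaten the primary safety endpoint.

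**What to change.** 1. **Labels, masking and batching (9.1, 9.2.1, 9.2.2, 9.2.3).** Keep the subject number and replace the collection date with a code whose key is held outside the assay laboratories. Read IHC masked to time point. Run each man's two samples on the same qPCR plate and in the same staining run.
2. **Analysis (10.3 item 1).** Summarize cores within man and time point. Report each man's change: log2(post/pre) normalized to RPLP0 for expression, and the absolute difference for IHC scores, which can be zero and so have no usable ratio. Add the mean change and its 95% interval. No per-marker significance tests are needed.
3. **Gene list (10.1, 10.3, 9.2.2).** Add NDRG1 primers or delete NDRG1, remove the open wording, and use the mean log2 change over the fixed set as the single AR-signaling summary.
4. **Wording (9.0).** Refer to the effect of the combination.

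Reconcile in the same edit: 10.1 and 10.3 list apoptosis by IHC, for which 9.2 describes no assay, while 2.3 and 9.2.1 specify Ki-67. Section 9.2.2 also normalizes to vehicle-treated cells, which have no counterpart in patient biopsies.

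Cost: wording, a code list, and a wait before the first sample of each pair is assayed. No extra patients, biopsies or staff are needed. Research tissue is already stored snap frozen (9.3), and a within-man change has to wait for the second sample in any case, so the delay is small.
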